4.8.2.1 Other Safety Analyses

Because of their importance in the studied patient population, COPD exacerbations will further be analyzed by severity (mild, moderate, and severe) based on commonly accepted clinical definitions as defined in GOLD 2018 Report. The count, percent of patients experiencing an event, and event rate per patient year of follow-up will be summarized overall and by severity.

4.9 Clinical Utility Analyses

Clinical utility, a secondary objective of the study, will be primarily assessed through the SGRQ, CAT, and post-procedure hospitalization rates. Details of the conduct of those analyses are provided below.

4.9.1 St. George's Respiratory Questionnaire (SGRQ)

SGRQ total score and changes from baseline will be summarized by scheduled time point using descriptive statistics. The mean, standard deviation (SD), median, and inter-quartile range (IQR) will be reported. Statistical testing to evaluate change from baseline using methods consistent with the statistical assumptions required to support the analyses may also be conducted for exploratory purposes. P-values from a Sign test corresponding to non-parametric approach to test whether the median differs from zero and confidence intervals will be reported.

CONFIDENTIAL:

This document and its contents are the property of Gala Therapeutics, Inc. Any use, reproduction or distribution without the written permission of Gala Therapeutics, Inc. is prohibited.

	TYPE: Clinical Trial Document	Document No:	CLN-0000X
	TITLE: CS003 Statistical Analysis Plan	Revision:	A
		Release Date:	
		DCN	Page 10 of 44

4.9.2 COPD Assessment Test (CAT)

CAT total score and changes from baseline will be summarized by scheduled time point using descriptive statistics. The mean, SD, median, and IQR will be reported. Statistical testing to evaluate change from baseline using methods consistent with the statistical assumptions required to support the analyses may also be conducted for exploratory purposes. P-values from a Sign test corresponding to non-parametric approach to test whether the median differs from zero and confidence intervals will be reported.

4.9.3 Hospitalization Rates

Hospitalization rates will be reported on a per-patient and per-event basis. The per-patient hospitalization rate is the proportion of patients who were re-admitted post-discharge, excluding the two Bronchial Rheoplasty procedures. An individual patient will only be counted once no matter how many times they are readmitted during the follow-up period. The total number of hospitalizations will also be reported along with the rate calculated as the number of events per patient-year of follow-up.

4.9.4 Other Endpoints

The following describes the analysis plan for other, prespecified, exploratory measures of clinical utility as defined in the study protocol and in Section 3.2.3 above.

Continuous variables (e.g., FEV1, FVC) will be summarized by mean, SD, median, and IQR. Categorical variables (e.g., responder rates) will be summarized by the number and percentage of patients in each of the corresponding categories. Statistical testing to evaluate change from baseline using methods consistent with the statistical assumptions required to support the analyses may also be conducted for exploratory purposes. P-values from a Sign test corresponding to non-parametric approach to test whether the median differs from zero and confidence intervals will be reported.

4.9.4.1 Responder Rates

The proportion of patients meeting the following improvement thresholds at follow-up will be summarized:

- at least 2-point decrease (improvement) in CAT total score
- at least 4-point decrease (improvement) in CAT total score
- at least 2-point decrease in the sum of the first two questions of the CAT

CONFIDENTIAL:

This document and its contents are the property of Gala Therapeutics, Inc. Any use, reproduction or distribution without the written permission of Gala Therapeutics, Inc. is prohibited.

	TYPE: Clinical Trial Document	Document No:	CLN-0000X
	TITLE: CS003 Statistical Analysis Plan	Revision:	A
		Release Date:	
		DCN	Page 11 of 44

- at least 2-point decrease in CAT total score and a 1-point decrease in either of the first two questions of the CAT
- at least 4-point decrease (improvement) in SGRQ total score
- at least 8-point decrease (improvement) in SGRQ total score

4.9.4.2 Cough and Sputum Assessment Questionnaire (CASA-Q)

CASA-Q scores for each domain and changes from baseline (cough symptom, cough impact, sputum symptom and sputum impact) will be summarized at each timepoint using descriptive statistics as described in Section 4.9.4 above.

4.9.4.3 Pulmonary function

Pulmonary function test results including forced vital capacity (FVC), forced expiratory volume one second (FEV₁), and FEV₁ / FVC ratio will be summarized using descriptive statistics as described in Section 4.9.4 above. Change from baseline to follow-up will also be summarized.

4.9.4.4 CT Scan

High-Resolution CT Scan (HRCT) scans will be performed at Baseline, 1 Month (prior to the second Bronchial Rheoplasty procedure), and 6 Months visits. Results of quantitative post-processing of the HRCTs including airway volume, total airway count, and lobar volumes will be summarized by visit. For each patient, the assessment from left and right lung will be averaged so each patient contributes one value for each timepoint. Changes from baseline to follow-up will also be summarized.

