7.2 Description of Visits

7.2.1 Visit #1. Screening and Enrollment

Subjects who meet the eligibility criteria and have signed an informed consent form may be enrolled in the study. Assessments performed exclusively to determine eligibility for this study will be done only after obtaining signed informed consent from the subject. Assessment performed for clinical indications (i.e., not exclusively to determine study eligibility) may be used for screening evaluation even if the studies were completed before informed consent was obtained.

All screening procedures must be completed within 90 days prior to start of study treatment.

Note: If the subject experiences a COPD exacerbation or other change in functional status between screening and the first bronchoscopy, screening procedures should be repeated as appropriate at the investigator's discretion. Refer to the Table 7.1 Schedule of Events for listing of required screening procedures.

General Screening Notes:

High Resolution CT Scan

High resolution computed tomography (HRCT) is incorporated as a tool to define subject inclusion criteria and to assess post treatment changes. CT acquisition will be per the CT Core Manual provided separately to each site upon completion of training by the designated CT core lab for this study.

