7.4 Schedule of Events (Table 7.1)

Table 7.1: Schedule of Events

	Visit #1: Screening	Visit #2: Bronchoscopy #1	Visit #3: Follow-up 1 week Post-Bronchoscopy #1	Visit #4: Bronchoscopy #2	Visit #5: Follow-up 1 week Post-Bronchoscopy #2	Visit #6: Follow-up 1 month Post-Bronchoscopy #2	Visit #7: Follow-up 3 month Post-Bronchoscopy #2	Visit #8: Follow-up 6 month Post-Bronchoscopy #2	Visit #9: Follow-up Phone Call 10 month Post-Bronchoscopy #2	Visit #10-14: Annual Follow-up 1 - 5 years Post-Bronchoscopy #2
Window			± 3 days	-3 to +6 weeks	± 3 days	± 7 days	± 2 weeks	± 4 weeks	± 2 weeks	± 4 weeks
Informed Consent	X									
Inclusion/Exclusion Criteria	X									
Medical History	X									
Exacerbations History	X	X	X	X	X	X	X	X	X	X
Concomitant Meds	X	X	X	X	X	X	X	X	X	X
Adverse Events		X	X	X	X	X	X	X	X	X
Physical Exam	X	X ¹	X	X ¹	X	X	X	X		X
CBC & Blood Panel	X	X ¹		X ¹			X	X		X
Cotinine Test	X									
EKG	X	X ⁴		X ⁴			X	X		X
Spirometry	X			X ¹			X	X		X
DLCO/Body Pleth	X			X ¹			X	X		X
Six Minute Walk Test	X									
CT Scan	X			X ¹				X		
Bronchoscopy		X		X						
Bronchoalveolar lavage		X		X						
RheOx Bronchial Rheoplasty		X		X						
Induced Sputum Sample	X						X	X		X
SGRQ	X			X ¹			X	X		X
CAT Score	X			X ¹			X	X		X
CASA-Q	X			X ¹			X	X		X
ISI ⁵	X			X ¹			X	X		X
Cough Counting Monitor ⁶	X						X	X		X ⁷
EXACT-PRO ⁸	X	DAILY								
Note 1:	Noted activities are completed prior to bronchoscopy.									
Note 2:	Adverse Events are noted before and after bronchoscopy.									
Note 3:	Overnight Hospital Stay at discretion of PI									
Note 4:	An EKG is recorded prior to the initiation of RheOx procedure and during at least one energy delivery; anesthesia EKG may be used.									
Note 5:	Subjects with clinically significant insomnia at baseline as defined by a ISI score of ≥ 8 points ²¹ , may be asked to complete optional polysomnography testing at baseline and 3-months follow-up.									
Note 6:	In this study, VitaloJAK cough monitor is an exploratory outcome measure. Patients willing to participate are encouraged to wear the 24 hour cough monitor at the 4 visits specified, but it is not mandatory.									
Note 7:	12-month visit only									
Note 8:	In this study, EXACT-PRO is an exploratory outcome measure to quantify and measure exacerbations of COPD. Patients are encouraged to complete the questionnaire daily during the first year (up to Visit #10), but it is not mandatory. Daily patient compliance will not be a reason for removal from the study.									

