4 STATISTICAL METHODOLOGY

4.1 Sample Size Determination

Since this is an early feasibility study, no formal sample size calculations were conducted. Up to 30 patients will be enrolled and treated with the study device to assess the effect of the investigational device in the target population. This sample size was based upon clinical judgement rather than statistical considerations.

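### CT airway change is tested against zero without using the lung volume from the same scans, so an average difference in inflation between visits would read as an airway effect

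*SAP*

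**What the plan says.** SAP 4.9.4.4 states that "Results of quantitative post-processing of the HRCTs including airway volume, total airway count, and lobar volumes will be summarized by visit". It then says that "For each patient, the assessment from left and right lung will be averaged so each patient contributes one value for each timepoint" and that "Changes from baseline to follow-up will also be summarized". For the exploratory endpoints as a group, SAP 4.9.4 adds: "P-values from a Sign test corresponding to non-parametric approach to test whether the median differs from zero and confidence intervals will be reported". The Table 14.2.6 shell follows this, with a p-value and 95% CI row for CT change.

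Neither document names a normalisation, a covariate or a check based on lung volume at the scan. Lobar volumes are listed as one more HRCT outcome (protocol 3.2.3, SAP 3.2.3), not as an adjustment variable. Protocol 7.2.1 deals with acquisition by reference: "CT acquisition will be per the CT Core Manual provided separately to each site". That manual is not among the documents.

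On size, SAP 4.1 says "Up to 30 patients will be enrolled and treated with the study device" and that "no formal sample size calculations were conducted". No SD or expected CT effect is given. Protocol 8.1 describes a single-arm, unblinded study.

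**The concern.** Airways widen, and more of them can be segmented, as the lung inflates. If patients on average hold a deeper breath at 6 months than at baseline, airway volume and count rise with no change in the airways themselves. If they hold a shallower one, a true gain is masked or a loss is suggested. A control arm would share such a shift and cancel it, but there is none here. The scans already yield the lobar volumes that would show whether inflation changed, and the plan does not use them for this purpose.

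At stake is the reading of an exploratory imaging result, which might be cited as evidence that the device acts on the airways. No decision rule in the plan depends on it.

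**Working it through.** The plan states no figure for CT change, so there is none to reproduce. The check asks how often the planned sign test would reject when the airways have not changed.

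**Inputs from the documents:** n = 30 at most (SAP 4.1); sign test of median change against zero (SAP 4.9.4). A two-sided 5% level is inferred from the 95% CI in Table 14.2.6.

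**Inputs assumed:** mean inflation shift d of 0, 3 or 5%; SD of inflation change s_L of 5 or 10%; exponent b linking airway volume to lung volume of 0.5 or 1; SD of all other change s_e of 5 or 10%.

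**Test.** With n = 30 the exact two-sided sign test rejects at 21 or more, or 9 or fewer, positive changes. Its actual level is 0.0428.

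**Model with no airway effect.** Airway change = b × (inflation change) + error, so

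P(change > 0) = Φ( b·d / √(b²·s_L² + s_e²) ).

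| Mean shift d | Case | b, s_L, s_e | P(change > 0) | Rejection |
|---|---|---|---|---|
| 0% | any | any | 0.500 | 4.3% |
| 3% | lowest | 0.5, 10%, 10% | Φ(0.015/0.1118) = 0.553 | 8% |
| 3% | highest | 1, 5%, 5% | Φ(0.030/0.0707) = 0.664 | 42% |
| 5% | lowest | 0.5, 10%, 10% | Φ(0.025/0.1118) = 0.588 | 15% |
| 5% | highest | 1, 5%, 5% | Φ(0.050/0.0707) = 0.760 | 84% |

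The first row matters: scatter in breath depth with no average shift leaves the error rate at 4.3%. Only a systematic shift produces false positives. Airway count was not modelled.

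**Would a per-litre ratio correct this?** On the log scale the ratio changes by (b − 1) × (log inflation change) + error. It is right only if b = 1. At b = 0.5 the coefficient is −0.5 instead of +0.5, so the ratio errs exactly as often as the raw analysis, in the opposite direction. With s_L = 8% and s_e = 5%, that is 15% at a 3% shift and 35% at a 5% shift.

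**What if treatment changes lung volume?** Take a true airway gain of 5% with SD 5%. Power of the ratio is 0.98 if lung volume is unchanged: Φ(ln 1.05/0.05). It falls to 0.36 if treatment also raises lung volume by 3%, and to 0.043 if it raises it by 5%.

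**Regression instead of a ratio.** Regressing airway change on lung-volume change estimates b from the data. Under the model above the intercept, which is the change at zero lung-volume change, has expectation zero whatever the shift. Its standard error is about s_e × √(1/n + d²/((n − 1)·s_L²)). With d, s_L and s_e all 5%, this is 0.05 × √(0.0333 + 0.0345) = 0.0130. The raw mean has 0.0707/√30 = 0.0129 if b = 1 and 0.0559/√30 = 0.0102 if b = 0.5. In this setting the adjusted estimate costs little or some precision, depending on b.

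**The case against.** The strongest reply is that inflation may already be controlled where we cannot see it. Breath-hold coaching and repeat-scan rules may be in the CT Core Manual, and the documents do not say whether the post-processing output is already scaled. Nothing in either document points to an average shift between visits. This stands: the gap is shown for the planned analysis, not for acquisition, and the shift is hypothetical. Showing total lung volume would also reveal whether standardisation worked.

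A second reply is that lobar volumes and their changes are to be summarised in any case, so a reader could notice a shift. Protocol Table 7.1 also schedules "DLCO/Body Pleth" at the three CT visits. This stands in part. Total lung volume is not a planned row, Table 14.2.7 covers only FEV₁, FVC and their ratio, and nothing links either volume measure to the airway result.

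Third, the endpoint is exploratory and unpowered, and lack of a control arm limits every change-from-baseline measure here. That is true, and it keeps the point minor.

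A reader might infer that any patient-level difference in breath depth invalidates the CT result in both directions, or that lobar volumes supply a free correction that should replace the raw p-value. The working supports neither. Scatter alone leaves the error rate at nominal, a fixed ratio can err as often as the raw test, and lobar volume is itself an outcome that treatment may change.

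**Conclusion.** The point holds in a limited form. The SAP tests raw CT airway change against zero and makes no use of lung volume from the same scan. In this single-arm study a systematic inflation difference between visits would therefore be read as an airway effect. For airway volume with n = 30, false rejection is about 8 to 42% at a 3% mean shift and about 15 to 84% at a 5% shift, against 4.3% with no shift. These ranges rest wholly on assumed shift, exponent and SDs, and acquisition control may make the true shift smaller or negligible. The documents do not support saying that the CT result is uninterpretable. It is a minor, inexpensive improvement to an exploratory analysis.

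**What to change.** In SAP 4.9.4.4 and Table 14.2.6:

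1. Keep the raw change from baseline as the main analysis.
2. Add total CT lung volume at each scan and its change from baseline. Define it as the sum of the lobes, and exempt it from the left/right averaging rule.
3. Pre-specify a sensitivity analysis: regress change in airway volume, and separately in airway count, on change in total lung volume. Report the mean change estimated at zero lung-volume change, with its CI. Do not use a fixed per-litre ratio.
4. State the limit: if treatment itself changes lung volume, the adjusted estimate removes part of a real effect, so it is read beside the raw result and does not replace it.

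The cost is SAP wording, a few table rows and one simple model per airway metric. All inputs come from scans and post-processing already planned.

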3.2.3 Other Endpoints

Other, tertiary and exploratory endpoints will also be assessed including changes from baseline to follow-up in;

- Responder rates utilizing established clinically meaningful thresholds for SGRQ (4 points)¹⁷ and CAT (2 points)¹⁶
- Change in other QOL measures including CASA-Q and EXACT-PRO
- Change in lung function as measured by FEV₁ and FVC
- Change in sleep patterns as assessed by the Insomnia Sleep Index (ISI)
- Change in cough count as assessed by a cough counting monitor
- Mucin concentrations (MUC5AC, MUC5B) from induced sputum samples
- Quantitative High Resolution CT Scan (HRCT) metrics including airway volume, total airway count, and lobar volumes
- Device performance

In addition to the endpoints described above, additional safety analyses in support of the primary study outcome and to assess the totality of safety profile of the RheOx Bronchial Rheoplasty, will be conducted.

Adverse events reported from the day of the index procedure through completion or termination of the study will be assessed. AEs and SAEs will be summarized using a standard medical coding dictionary (MedDRA). AEs and SAEs will be also analyzed by severity, relatedness to the device and/or procedure and within discrete time periods relative to the index procedure.

COPD exacerbations will also be analyzed by severity (mild, moderate, and severe) based on commonly accepted clinical definitions as defined in GOLD 2018 Report¹⁸.

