7.1 Treatment Plan

Following screening and enrollment, subjects will undergo two bronchoscopic procedures (Visit 2 and Visit 4) both of which include treatment with the investigational device. Bronchoalveolar Lavage (BAL) will also be completed during the bronchoscopy prior to the initiation of RheOx treatment.

Investigational treatment with RheOx will be administered to the right lung during bronchoscopy #1 (Visit 2) and to the left lung during bronchoscopy #2 (Visit 4). Each activation will deliver 5 packets of electrical pulses synchronized with the cardiac cycle such that 1 packet is delivered with each cardiac cycle.

The IVY cardiac monitor will be utilized to monitor cardiac activity during the RheOx Bronchial Rheoplasty in this study. The IVY will be set with heart rate alarm limits of less than 30 beats per minute (BPM) and greater than 130 BPM. Anesthesiologists assigned to the study will be trained on IVY alarm signal and its indication. Anesthesiologists will be instructed to use their best clinical judgement and follow standard of care procedure should the IVY monitor alarm during the bronchoscopy procedure.

The total number of activations is at the discretion of the treating physician in order to completely treat accessible airways in the designated treatment areas. The number of activations is dependent upon patient anatomy including airway diameter, airway length and airway accessibility and typically range between 30 and 60 activations per lung. In some cases, bronchoscopists may be able to access more distal subsegmental airways, delivering additional activations occasionally totaling over 100 activations.

Note:

A therapeutic bronchoscope having at least a 3.0 mm working channel, such as the Olympus model 1T180, is required for use with the RheOx Catheter.

Specimen/fluid from the BAL is used to assess pathogens and cell composition in the airways as well as markers for inflammation. Samples will be collected at each bronchoscopy and compared to determine whether any changes occur after the use of RheOx. BAL instructions are included in the study operational instruction manual.

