10.1.3 Unanticipated Adverse Device Effect

An investigator shall submit to the sponsor a report of any unanticipated adverse device effect occurring during an investigation as soon as possible, but in no event later than 10 working days after the investigator first learns of the effect.

Reports relating to the patient's subsequent medical course must be submitted to the Sponsor via the study eCRFs until the event has subsided or, in case of permanent

impairment, until the event stabilizes, and the overall clinical outcome has been ascertained. For reported deaths, the investigator should supply the Sponsor and the IRB with any additional requested information (e.g., autopsy reports and terminal medical reports).

The Sponsor is responsible for reporting all serious and unexpected adverse device effects to FDA in an expedited manner, and in accordance with all applicable federal regulations. The Sponsor will expedite the reporting in compliance with ICH GCP to all concerned investigators. The investigator will report to the IRB in accordance with institutional requirements, but no later than 7 calendar days of first knowledge.

10.2 List of foreseeable adverse events related to investigational therapy and/or study procedure:

- Sore throat (likely occurrence)
- Coughing (likely occurrence)
- Hemoptysis (likely occurrence)
- Minor complications associated with anesthesia (moderate likely occurrence) including nausea, vomiting, bruising at the site of injections, sore throat or hoarse voice, urinary retention
- Infection (moderately likely occurrence) including fever, pain or soreness
- Exacerbation (moderately likely occurrence) including shortness of breath, increased color and/or quantity of phlegm
- Bronchial perforation (low occurrence)
- Lung abscess (low occurrence)
- Gastroparesis (low occurrence)
- Pneumothorax (low occurrence) including severe chest pain, trouble breathing, death
- Airway stenosis (low occurrence) including wheezing, hoarseness, shortness of breath and/or respiratory distress
- Abnormal cardiac rhythm function (low occurrence) including arrhythmia, atrial fibrillation, ventricular fibrillation, death
- Allergic reaction (low occurrence) including abnormal breathing, difficulty swallowing, anxiety, chest pain, severe cough, lightheadedness or dizziness, sweating or fainting, swelling of the face, eyes or tongue
- Significant pulmonary bleeding (low occurrence)

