[5] All concomitant medications after 12 months through 5 years after Bronchial Rheoplasty 2.

CONFIDENTIAL:

	TYPE: Clinical Trial Document	Document No:	CLN-0000X
	TITLE: CS003 Statistical Analysis Plan	Revision:	A
		Release Date:	
		DCN	Page 26 of 44

Table # 14.2.4 Quality of Life Outcomes through 12 Months
Evaluable Population

Parameter (CAT, SGRQ, CASA-Q)	Baseline	1 Month	3 Months	6 Months	12 Months
Observed value					
N	xx	xx	xx	xx	xx
Mean (SD)	xx.x (x.xx)	xx.x (x.xx)	xx.x (x.xx)	xx.x (x.xx)	xx.x (x.xx)
Median (IQR)	xx.x (xx.x, xx.x)	xx.x (xx.x, xx.x)	xx.x (xx.x, xx.x)	xx.x (xx.x, xx.x)	xx.x (xx.x, xx.x)
Min, Max	xx.x, xx.x	xx.x, xx.x	xx.x, xx.x	xx.x, xx.x	xx.x, xx.x
Change from Baseline					
N		xx	xx	xx	xx
Mean (SD)		xx.x (x.xx)	xx.x (x.xx)	xx.x (x.xx)	xx.x (x.xx)
Median (IQR)		xx.x (xx.x, xx.x)	xx.x (xx.x, xx.x)	xx.x (xx.x, xx.x)	xx.x (xx.x, xx.x)
Min, Max		xx.x, xx.x	xx.x, xx.x	xx.x, xx.x	xx.x, xx.x
Pvalue (95% CI)		x.xx (x.xx, x.xx)	x.xx (x.xx, x.xx)	x.xx (x.xx, x.xx)	x.xx (x.xx, x.xx)

CONFIDENTIAL:

	TYPE: Clinical Trial Document	Document No:	CLN-0000X
	TITLE: CS003 Statistical Analysis Plan	Revision:	A
		Release Date:	
		DCN	Page 27 of 44

Table # 14.2.5 Quality of Life Outcomes Post 12 Months
Evaluable Population

Parameter (CAT, SGRQ, CASA-Q)	2 Years	3 Years	4 Years	5 Years
Observed value				
N	xx	xx	xx	xx
Mean (SD)	xx.x (x.xx)	xx.x (x.xx)	xx.x (x.xx)	xx.x (x.xx)
Median (IQR)	xx.x (xx.x, xx.x)	xx.x (xx.x, xx.x)	xx.x (xx.x, xx.x)	xx.x (xx.x, xx.x)
Min, Max	xx.x, xx.x	xx.x, xx.x	xx.x, xx.x	xx.x, xx.x
Change from Baseline				
N	xx	xx	xx	xx
Mean (SD)	xx.x (x.xx)	xx.x (x.xx)	xx.x (x.xx)	xx.x (x.xx)
Median (IQR)	xx.x (xx.x, xx.x)	xx.x (xx.x, xx.x)	xx.x (xx.x, xx.x)	xx.x (xx.x, xx.x)
Min, Max	xx.x, xx.x	xx.x, xx.x	xx.x, xx.x	xx.x, xx.x
Pvalue (95% CI)	x.xx (x.xx, x.xx)	x.xx (x.xx, x.xx)	x.xx (x.xx, x.xx)	x.xx (x.xx, x.xx)

CONFIDENTIAL:

	TYPE: Clinical Trial Document	Document No:	CLN-0000X
	TITLE: CS003 Statistical Analysis Plan	Revision:	A
		Release Date:	
		DCN	Page 28 of 44

Table #14.2.6 HRCT Scan Quantitative Analysis
Evaluable Population

Visit/ Statistics	Baseline	1 Month	6 Months
Parameter			
Observed Value			
N	xx	xx	xx
Mean (SD)	xx.x (x.xx)	xx.x (x.xx)	xx.x (x.xx)
Median (IQR)	xx.x (xx.x, xx.x)	xx.x (xx.x, xx.x)	xx.x (xx.x, xx.x)
Min, Max	xx.x, xx.x	xx.x, xx.x	xx.x, xx.x
Change from Baseline			
N		xx	xx
Mean (SD)		xx.x (x.xx)	xx.x (x.xx)
Median (IQR)		xx.x (xx.x, xx.x)	xx.x (xx.x, xx.x)
Min, Max		xx.x, xx.x	xx.x, xx.x

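### SAP 4.9.4.4 averages left and right lung for every CT metric, so a total airway count would print as half the total and lobar volumes would lose their lobe

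*SAP*

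**What the plan says.** Protocol 3.2.3 lists among the other, exploratory endpoints "Quantitative High Resolution CT Scan (HRCT) metrics including airway volume, total airway count, and lobar volumes". It mentions no averaging across lungs.

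SAP 4.9.4.4 schedules the scans at "Baseline, 1 Month (prior to the second Bronchial Rheoplasty procedure), and 6 Months visits" and says that results "including airway volume, total airway count, and lobar volumes will be summarized by visit". The next sentence adds that, for each patient, "the assessment from left and right lung will be averaged so each patient contributes one value for each timepoint". No metric is exempted. The section does not say how several lobes become one value for a lung.

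Nothing else in the SAP restores side or lobe. The shell for Table 14.2.6, "HRCT Scan Quantitative Analysis", has one generic parameter block by visit, with no row or column for lung or lobe. The four planned listings (disposition, deviations, concomitant medications, adverse events) include none for CT.

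**The concern.** The three metrics differ in kind, and one combining rule does not suit all of them. A total is a sum, so averaging two lungs does not give it. Lobar volumes are a set of named quantities, and reducing them to one number per patient removes what the name promises. Read literally, the SAP does not deliver two of the three metrics that the protocol names, and two programmers could derive different lobar results from the same scans.

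The stated aim, one value per patient, does not call for averaging. A sum over both lungs, or each lobe treated as its own parameter, also gives one value per patient and timepoint.

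Two things are at stake: the row label in Table 14.2.6 would not match its content, and a change confined to one lung or one lobe would appear smaller than it is. By Protocol Table 7.1, the 6-month CT is the only one scheduled after both lungs have been treated.

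**Working it through.** The documents give no numeric CT result or CT power calculation, so there is no figure to reproduce. The rule itself can be checked by arithmetic. The airway counts, lobe volumes and losses below are assumptions for illustration.

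**1. Total airway count, if supplied per lung.** With R and L the counts in each lung and T = R + L, the planned value is (R + L)/2 = T/2.

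- Assume R = 110 and L = 100. Then T = 210 and the planned value is 105.
- A true change of −20 airways prints as −10. The SD of the change and both confidence limits are halved in the same way.
- Percent change is (ΔT/2)/(T/2) = ΔT/T, so it does not move. The sign of each patient's change does not move either, so the sign-test p-value is the same.

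If the core lab supplies only one count for the whole patient, there is no left and right value and the rule cannot be applied.

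**2. A change in one lung only.** Assume the right lung loses 20% of its airways: 110 × 0.20 = 22. The planned value changes by −11. In relative terms that is −22/210 = −10.5%. A sum over both lungs also gives −10.5%, so summing corrects the label but not the dilution. Only separate right and left rows show the −20%.

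**3. Lobar volumes.** The right lung has three lobes and the left has two. Upper and lower lobes can be paired across sides; the right middle lobe cannot. The sentence admits at least three readings. Assumed volumes are 1000, 450 and 1200 mL on the right (sum 2650) and 1100 and 1050 mL on the left (sum 2150), with a 300 mL loss in one lobe and no change elsewhere.

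| Reading | Loss in a right lobe | Loss in a left lobe |
|---|---|---|
| A: sum lobes within each lung, then average lungs | 300/2 = 150 mL | 300/2 = 150 mL |
| B: average lobes within each lung, then average lungs | 300/3/2 = 50 mL | 300/2/2 = 75 mL |
| C: average upper with upper and lower with lower | 300/2 = 150 mL for that pair; middle lobe undefined | 300/2 = 150 mL for that pair |

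For the 1000 mL lobe the true loss is 300/1000 = 30%. Under A the baseline value is (2650 + 2150)/2 = 2400 mL and the printed change is −150/2400 = −6.3%. Under B the baseline is (883.3 + 1075)/2 = 979.2 mL and the change is −50/979.2 = −5.1%. Under C it is −150/1050 = −14.3%; the lobe level survives but the side is lost.

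**4. Offset by an opposite change.** Suppose another lobe gains the same 300 mL.

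- Reading A: −150 + 150 = 0, whichever lung gains.
- Reading B, gain in the same lung: −50 + 50 = 0 on the right, and −75 + 75 = 0 on the left.
- Reading B, gain in the other lung: −50 + 75 = +25 mL for a right-lobe loss, and −75 + 50 = −25 mL for a left-lobe loss.

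So offset is possible, but its size depends on the reading and on where the gain occurs.

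**The case against.** The strongest reply is that this is a matter of labelling and derivation in an exploratory table on which no decision rests. Much of that stands. CT metrics are in neither the primary safety outcome nor the secondary endpoints, and the study is unpowered and descriptive. Halving a count is a change of scale and distorts no test. The halving is also conditional: the SAP does not say whether counts arrive per lung, and the core lab manual that Protocol 7.2.1 refers to is not part of these documents. Table 14.2.6 is a generic shell, and a programmer might repeat its block for each lobe pair, as in reading C.

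A reader might go further and infer that the averaging would hide a treatment-related stenosis. Protocol 10.2 does list "Airway stenosis (low occurrence) including wheezing, hoarseness, shortness of breath and/or respiratory distress". But it puts low-occurrence events below 1 in 100 patients, so fewer than 30 × 0.01 = 0.3 cases would be expected in 30 patients. One patient losing 300 mL in one lobe would move even that lobe's own 30-patient mean by only 300/30 = 10 mL. A group summary is not a detector of single cases under either rule, and a recognised stenosis would be reported, coded and tabulated as an adverse event.

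The objection does not remove the written rule. It applies to all three metrics, gives half a total where per-lung counts exist, and leaves lobar volumes without at least their side.

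**Conclusion.** The point holds, at modest weight. As written, SAP 4.9.4.4 does not deliver the total airway count or the lobar volumes named in Protocol 3.2.3. With per-lung counts, the total row prints at exactly half size in absolute terms; with a whole-patient count only, the rule cannot be applied. For lobar volumes, a single value per patient is no longer lobar, and a one-lobe change prints at between one sixth and one half of its absolute size, depending on the reading. These fractions follow from the rule and the number of lobes in each lung. The millilitre and percentage examples rest on assumed volumes and losses.

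Three stronger conclusions that a reader might draw are not supported: that the count is certainly wrong by a factor of two, that exploratory test results for the count are distorted, and that any compensated loss prints as zero. The first depends on the form of the core lab output, the second fails because the sign test ignores scale, and the third fails under reading B when the gain is in the other lung.

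**What to change.** Replace the averaging sentence in SAP 4.9.4.4 with:

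> Total airway count is the sum over both lungs; airway count and airway volume are also summarised for the right and left lung separately where the core lab output provides them. Lobar volumes are summarised separately for each of the five lobes, as observed value and change from baseline.

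Add these rows to Table 14.2.6, with the lobe rows descriptive only and without p-values, so that the number of unadjusted exploratory tests does not grow with them. I would not list each patient's largest single-lobe fall, because that picks the extreme of five noisy changes and would tend to show decreases from noise alone.

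The cost is a longer exploratory table. No new scans are needed, and lobe-level values must already exist if lobar volumes are to be reported. The documents do not show that counts and airway volume are available by side, so those rows are conditional. Where they are available, they also separate the treated right lung from the not yet treated left lung at the scan taken before the second procedure.
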